#### **Recruitment**

Subjects will be recruited from among:

- (i) The test sites' pool of existing and new clients
- (ii) Subjects who respond to the following IRB-approved recruitment materials:

#### **Compensation**

Subjects will not receive financial payment or any other form of compensation to participate in this study. Subject will not be charged for the cost of the Violet ZERONA® Z6 OTC treatments or for the cost of any other evaluations or measurements that occur as part of his or her participation in the study.

## **STUDY PROCEDURES**

Investigators / device user in this clinical study will be required to follow all procedures contained within SECTION 3: VIOLET ZERONA Z6 OTC OPERATION of the Violet ZERONA® Z6 OTC Installation and Proper Use Reference Guide, pages 15 through 27, without any additional guidance, materials, instruction, whether verbal or written or otherwise, from any source, as per real-life intended use.

SECTION 3 of the Violet ZERONA® Z6 OTC Installation and Proper Use Reference Guide includes the following:

- 1. Violet ZERONA Z6 OTC Operation: pages 15 23
- 2. Violet ZERONAT Z6 OTC Treatment Protocol: page 24
- 3. Violet ZERONA Z6 OTC Client Qualification Checklist: pages 25 28: includes protocols for calculation of:
  - Body Mass Index (BMI): pages 26 27; and
  - Body circumference measurements (waist, hips, and thighs): page 28

#### PRE-PROCEDURE ACTIVITIES

All pre-procedure activities will take place on the same day and proceed successively as follows:

#### SIGNING OF INFORMED CONSENT FORM

The investigator / device user will commence by presenting and reviewing in detail the items in the informed consent form with the individual and answer any questions. To proceed further in the study protocol, the individual must willingly sign the informed consent form at this time.

#### ASSIGNMENT OF SUBJECT ID

The subject will be assigned a unique non-identifying Subject ID composed of the Investigator's / user's first and last name initials and a 3-digit number based upon the subject's order of entry into the study.

#### INCLUSION/ EXCLUSION CATERIA

The investigator / user conducts the CLIENT QUALIFICATION CHECKLIST as contained in the Installation and Proper Use Reference Guide, to determine if the client is suitable for the Violet ZERONA® Z6 OTC treatment. As part of this assessment, the investigator / user conducts the BMI evaluation. The CLIENT QUALIFICATION CHECKLIST includes PART A and PART B as follows:

- **A. CLIENT QUESTIONS:** The client will be asked to respond "YES or NO" to the following questions:
- Are you under 18 years of age?
- (Female clients only): Are you pregnant or do you think you might be pregnant? Not applicable, client is male
- Do you have any open wounds (sores, cuts, ulcers, etc.)?
- Do you have or are you being treated for any cancerous growths?

A client that answers "**YES**" to one or more of the client questions is not suitable for the treatment with the Violet ZERONA® Z6 OTC. A client that answers "**NO**" to ALL the questions will proceed to the Body Mass Index (BMI) Calculation.

#### B. BODY MASS INDEX (BMI) CALCULATION:

- BMI is 30 or less => the client qualifies for Violet ZERONA Z6 OTC treatment.
- BMI is more than 30 => the client does not qualify for Violet ZERONA Z6 OTC

#### PRE-PROCEDURE STUDY MEASUREMENTS

A subject who satisfies the criteria to receive the study treatment per the Client Qualification Checklist will complete the following pre-procedure study assessments:

*Circumference Measurements* of the waist, hips, and thighs per the instructions contained in SECTION 3: VIOLET ZERONA® Z6 OTC OPERATION of the Installation and Proper Use Reference Guide, under the MEASUREMENT PROTOCOL & MEASUREMENT AREAS header on page 28.

#### PROCEDURE ADMINISTRATION ACTIVITIES

The procedure administration phase of the study will commence immediately following completion of the pre-procedure activities, on the same day. The first treatment administration with the Violet ZERONA® Z6 OTC will be administered that day.

The investigator / device user is required to follow the instructions in SECTION 3: VIOLET ZERONA® Z6 OTC OPERATION of the Erchonia Violet ZERONA® Z6 OTC Installation and Proper Use Reference Guide to correctly administer a procedure.

The procedure administration protocol in this current study is identical to that evaluated in the 2014 comparative study, with the exception being that the treatment time with the violet laser is 20 minutes compared to 40 minutes with the red laser. However, as the timing is automatically pre-programmed in the laser device, and it beeps and pauses automatically mid-treatment to enable the individual to turn-over and the laser arms to be resituated to the posterior aspect of the patient, and subsequently automatically shuts off when the second half of the treatment is completed, this has no impact on the user's operation of the Violet ZERONA® Z6 OTC device compared with the ZERONA® Z6 OTC device.

Both the predicate and the currently evaluated laser devices have the same treatment protocol: 6 treatments occurring over 2 weeks: 3 treatments per week; each treatment every other day.

#### PROCEDURE ASSESSMENTS

After completion of the sixth and final scheduled Violet ZERONA® Z6 OTC treatment administration, the investigator / user will again record the subject's BMI and waist, hips and thighs circumference following the protocols in the Installation and Proper Use Reference Guide.

This is considered the study endpoint evaluation at which change relative to pre-procedure measurements will be assessed. Evaluation for and recording of any observed or reported adverse events will be conducted at each study visit.

## STATISTICAL ANALYSIS PLAN

#### **STUDY POPULATIONS**

The following two study populations will be evaluated:

#### 1. Modified Intent-to-Treat (mITT) Population

Primary analysis of efficacy will be according to the modified intent to treat (ITT) analysis, including all enrolled subjects who had a valid baseline visit and received at least the first study treatment with the Erchonia Violet ZERONA® Z6 OTC.

Missing data for the mITT population will be handled through Last Observation Carried Forward (LOCF) methodology. Sensitivity analysis may be applied if missing data is extensive.

#### 2. Per Protocol Population.

Secondary analysis of efficacy to confirm the findings of the primary analysis will be conducted on the per protocol population, comprised of all subjects who completed the study per protocol through to the final treatment administration and outcomes measures recording visit.

#### PRIMARY EFFICACY OUTCOME

The primary efficacy outcome for this clinical study is the mean change in combined waist-hipsbilateral thighs circumference measurement at study endpoint (following completion of the sixth and final treatment administration procedure) relative to baseline (pre-procedure).

#### PRIMARY EFFICACY OUTCOME EVALUATION

To determine primary efficacy outcome success, the mean change across all subjects enrolled in this study in combined waist-hips-bilateral thighs circumference measurements at study endpoint relative to baseline will be calculated and compared to the relative mean change attained for treated subjects in the reference study.

As this study is a non-inferiority design, the research hypothesis is that violet diode therapy with the Erchonia Violet ZERONA® Z6 OTC is either equivalent to, or superior to, red diode therapy with the Erchonia Zerona® Z6 OTC in effecting a clinically meaningful reduction in body circumference.

The selected equivalence margin ( $\delta$ ) is ±5%. Therefore, non-inferiority will be established if the mean change in combined circumference measurement for subjects treated with the violet diode laser in the current study is no more than 5% less than the subject group who received treatment with the red diode laser in the predicate reference trial that supported efficacy of the Zerona® Z6 OTC device (K143007).

In the predicate reference study, the mean change in combined circumference measurements across the same 6-treatment 2-week evaluation period was a decrease of 3.72 inches. Therefore, success for the current study will be determined as having been met if the mean change in combined circumference measurements for the subject group in the current study is  $-3.72\pm5\%$  inches (-3.53 to -3.91 inches). This is defined as the maximally clinically acceptable difference for which the range of efficacy values ( $\pm5\%$ ) are "close enough" to be considered equivalent.

Version 1.0

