# REGULATORY BACKGROUND AND JUSTIFICATION FOR THE CURRENT STUDY

The intended regulatory pathway to seek clearance for the Erchonia Violet ZERONA® Z6 OTC for the intended indication is through a 510(k) submission with supportive clinical data from the outcome of this clinical study protocol.

The intended predicate device is the Erchonia ZERONA® Z6 OTC, previously FDA cleared under K162578.

The Erchonia ZERONA® Z6 OTC is currently FDA cleared under K162578 for use as a non-invasive dermatological aesthetic treatment for the reduction of body circumference. It is cleared for Over-the-Counter (OTC) use.

Preceding its clearance under K162578, the Erchonia Zerona® Z6 OTC received FDA clearance under K143007 for use as a non-invasive dermatological aesthetic treatment for the reduction of circumference of hips, waist, and thighs. K143007 was supported by the results of a Human Factors Validation and Testing Study that evaluated the lay user's ability to operate the device safely, correctly, and effectively per the instructions in the User's Manual. In that study, 22 lay user subjects administered the treatment with the Zerona® Z6 OTC to 22 client subjects. The outcome of that study demonstrated that the lay users successfully understood the information in the User's Manual and were able to follow the instructions to operate the device and administer treatments safely, correctly, and effectively. All treated subjects in that study received an active course of 6 treatments across 2 weeks administered by the lay users. The mean circumference reduction across the waist, hips and bilateral thighs for those subjects was -3.7 inches, a statistically significant finding of equivalency to the precedent prospective randomized controlled trial (RCT) evaluating efficacy of the Erchonia ZERONA® for noninvasive circumference reduction of the waist, hips, and bilateral thighs. In that prior study, 67 males and females aged 18 to 65 years received the identical treatment protocol of 6 treatments with the Zerona® equally spaced across 2 weeks to the waist, hips, and bilateral thighs. The 35 subjects who received the active laser treatment attained an average total circumference reduction of 3.5 inches compared with a mean decrease of 0.68 inches for the 32 subjects who received the sham treatment.

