## STUDY DESIGN

This clinical study is an open-label single-arm non-inferiority design to evaluate the efficacy of the Erchonia Violet ZERONA® Z6 OTC in providing noninvasive body circumference reduction. As such, all enrolled subjects will receive the active study treatment, and therefore, neither randomization to procedure group nor blinding of the subjects nor investigative parties is applicable.

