#### STUDY BLINDING

As all subjects in this study will receive the active procedure administration with the Erchonia Violet ZERONA® Z6 OTC, it is not possible to blind either subjects or investigators (device users).

However, there are two aspects of this study design that assist in supporting elements of blinding:

- (i) The primary efficacy study outcome assessment of body circumference measurements is objective; and
- (ii) As the outcome data from this current study will be comparatively assessed to that of the active treatment group in the predicate device clinical study (the clinical data for the Zerona® Z6 OTC submitted in support of K143007), it is possible to blind the study statistician as to which data set pertains to which study, as the variables for each will be identical. The data from each study will be de-identified and presented to the study statistician simply as 'Group A' and 'Group B' data. The statistician will not be aware of which group A or B contains the current study data and which contains the comparative data. The study statistician will also not be made aware of sample sizes for either analysis group if there is a difference. In this way, study success analysis by the statistician cannot be biased.

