#### Rationale for Sample Size

Sample size is determined to be identical to the final sample size treated and evaluated in the 2014 Zerona® Z6 OTC comparative study to enable clinically meaningful statistical comparison of outcomes to be performed.

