#### Hypotheses

• *Null Hypothesis*: Treatment application of the Erchonia Violet ZERONA® Z6 OTC is inferior to treatment application of the Erchonia® Zerona® Z6 OTC in effecting a clinically meaningful reduction in body circumference.

Ho:  $\mu$  < -3.53 inches

• *Alternative Hypotheses*: Treatment application of the Erchonia® Violet ZERONA® Z6 OTC is NOT inferior to treatment application of the Zerona® Z6 OTC in effecting a clinically meaningful reduction in body circumference.

H1:  $\mu \ge -3.53$  inches

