#### SUPPORTIVE SECONDARY EVALUATIONS

The following two secondary evaluations will be performed to provide direct support for the primary efficacy evaluation outcome are will therefore be assessed with respect to statistical significance of change and/or against pre-determined non-inferiority success criteria.

- (i) T-test for independent samples will be performed to compare the mean change in combined circumference measurements across study evaluation (at endpoint relative to baseline) for subjects treated with the Violet ZERONA® Z6 OTC in the current study to the relative mean change for subjects treated with the ZERONA® Z6 OTC in the reference study treatment group. i.e., between device treatment groups. A finding of the difference being not statistically significant (p>0.05) will provide statistically significant and clinically meaningful support for the equivalency of the efficacy of the two devices.
- (ii) Responder rate analysis will be conducted wherein individual responder success is defined per the reference study as at least a 3.0-inch reduction (≥-3.0 inches) in combined circumference measurements for the waist, hips, and bilateral thighs from baseline to after study treatment completion. The maximally clinically acceptable difference for which the responder rate for the current study subject group is defined is (±5%), that is, 73% +/- 5% (68% - 78%), as the responder rate attained in the reference study was 73%.

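### The primary rule declares non-inferiority from the observed mean alone, with no confidence limit, test or alpha; a device exactly at the margin passes about half the time.

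*Combined protocol and SAP*

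**What the plan says.** The Study Design section states: "This clinical study is an open-label single-arm non-inferiority design". The comparator is the 2014 red-diode study, in which, according to Regulatory Background, "22 lay user subjects administered the treatment with the Zerona® Z6 OTC to 22 client subjects".

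Primary Efficacy Outcome Evaluation sets a 5% margin around a reference mean change of -3.72 inches and gives two success rules:

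- One-sided: "non-inferiority will be established if the mean change in combined circumference measurement for subjects treated with the violet diode laser in the current study" is at most 5% below that of the reference group.
- Band: "success for the current study will be determined as having been met if the mean change in combined circumference measurements" lies between -3.53 and -3.91 inches.

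The Hypotheses section states the null as "Treatment application of the Erchonia Violet ZERONA® Z6 OTC is inferior to treatment application of the" red-diode device and writes it as mu < -3.53. The alternative is mu ≥ -3.53. No test statistic or significance level follows.

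The only inferential test on this endpoint is the independent-samples t-test in Supportive Secondary Evaluations, item (i). Of it the SAP says: "A finding of the difference being not statistically significant (p>0.05) will provide statistically significant and clinically meaningful support" for equivalency of the two devices.

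Rationale for Sample Size matches the new study to the reference study's final number "to enable clinically meaningful statistical comparison of outcomes to be performed". It states no power, alpha or SD.

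**The concern.** A non-inferiority conclusion should rule out, with a stated error rate, a true shortfall as large as the margin. A rule that looks only at the observed mean controls no error rate. The result would support a 510(k) submission, and this is its only primary success criterion.

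The other elements do not fill the gap:

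- The two success rules disagree for any mean beyond -3.91. It satisfies the first and fails the second, although the research hypothesis in the same section allows superiority.
- For a change score where more negative is better, mu < -3.53 is a larger reduction, so the written null is the favourable outcome.
- Reading p>0.05 as equivalence rewards small or noisy samples.
- Masking the statistician to group (Study Blinding) guards against analyst bias, not sampling error.

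**Working it through.** **Inputs from the document.** Reference mean -3.72 inches and margin 5% (Primary Efficacy Outcome Evaluation); 22 reference subjects (Regulatory Background); at least 22 new completers (Sample Size); 73% of reference subjects with a reduction of at least 3.0 inches (Supportive Secondary Evaluations, item (ii)).

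**The plan's own figures.** 3.72 × 0.95 = 3.534 and 3.72 × 1.05 = 3.906, which reproduce -3.53 and -3.91. The margin is 0.05 × 3.72 = 0.186 inches.

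**Result that needs no SD.** P(observed mean ≤ -3.53 | true mean -3.53) = Φ(0) = 0.50 for any SD and n. It needs only a symmetric sampling distribution of the mean; marked skew at n = 22 moves it to roughly 47% to 53%.

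**Assumed SD for the rest.** The document gives none. If reference changes are normal with mean -3.72 and 73% at or beyond -3.0, then SD = (3.72 - 3.0)/z(0.73) = 0.72/0.6128 = 1.175 inches. With n = 22, SE = 1.175/√22 = 0.251. Ranges below cover SD 0.8 to 2.0 (SE 0.171 to 0.426).

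**Probability of passing**, taking -3.72 as fixed, as the plan does:

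- One-sided: Φ((-3.53 - μ)/SE)
- Band: the same minus Φ((-3.91 - μ)/SE)

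| True mean μ | One-sided | Band |
|---|---|---|
| -3.53 (at the margin) | 0.500 (any SD) | 0.435 (0.314 to 0.487) |
| -3.348 (10% worse) | 0.234 (0.143 to 0.335) | 0.221 (0.142 to 0.247) |
| -2.976 (20% worse) | 0.013 (0.001 to 0.097) | 0.013 (0.001 to 0.083) |
| -3.72 (identical) | 0.776 (0.672 to 0.867) | 0.552 (0.344 to 0.735) |
| -4.092 (10% better) | 0.988 (0.906 to above 0.999) | 0.221 (0.142 to 0.247) |

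So an identical device fails 22% of the time under the one-sided rule and 45% under the band. A device 10% better fails the band 78% of the time.

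**Secondary t-test.** With 22 per group, df 42 and the noncentral t distribution, the chance of p>0.05 is:

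- true shortfall 0.186 (the margin): 92% (88% to 94%)
- true shortfall 0.372 (10%): 82% (67% to 91%)
- true shortfall 0.744 (20%): 46% (15% to 77%)

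**What a confidence interval could show.**

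- Half-width for violet minus red: t(0.975, 42) × SD × √(2/22) = 2.018 × 1.175 × 0.3015 = 0.715 inches (0.487 to 1.217), which is 2.6 to 6.5 times the 0.186-inch margin.
- Power for identical devices at that margin, one-sided 0.025: 7% (5% to 11%).
- With unlimited new subjects the reference SE remains: Φ(0.186/0.251 - 1.96) = 11% (6% to 19%).
- Observed violet mean needed: -3.72 + 0.186 - 0.715 = -4.25 inches (-4.02 to -4.75).

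**The case against.** The strongest reply is that the rule is mislabelled rather than dangerous. At an observed mean of -3.53 and SD 1.175, the single-arm 95% upper limit is -3.53 + 2.080 × 0.251 = -3.01 inches. That is far beyond the 0.68-inch sham decrease in the earlier randomised trial and close to the plan's 3.0-inch responder threshold. With the reference mean estimated as well, a pass tolerates a difference of about 0.19 + 0.715 = 0.90 inches, or 24% of 3.72 (18% to 38%). This stands: a device 20% worse rarely passes. But it also shows that the effective margin is several times the 5% claimed.

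Three further points have some force:

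- The inequalities may be loose notation, since the responder definition also writes ≥ for a larger reduction. The intent is then clear, but the hypotheses as written are still wrong.
- Expected Results and the research hypothesis favour the one-sided reading, so the band figures may describe an unintended rule. The band is nevertheless the explicit success statement.
- The SD is inferred from a responder percentage in 22 subjects. The 50% result, the missing alpha, the conflicting rules and the p>0.05 reading do not depend on it.

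**Conclusion.** The concern holds and needs correction before the data are analysed. The primary rule controls no error rate: a device exactly at the margin passes 50% of the time under the one-sided wording (given a roughly symmetric sampling distribution), where a conventional 95% interval rule would hold this to 2.5%. Under the band the figure is 44%, on normality and an assumed SD of 1.175 inches. The weakness lies at and near the margin; the rule does not readily pass a much worse device. Neither the hypotheses nor the t-test repairs it. At a 5% margin, 22 subjects against 22 cannot support the claim on any SD in the range examined.

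**What to change.** 1. **Primary rule.** Conclude non-inferiority only if the upper limit of the two-sided 95% confidence interval for violet minus red mean change, from both studies' subject-level data, is below +δ. The sponsor should state δ in inches and justify it before analysis.
2. **Direction.** Make the rule one-sided, so that a mean reduction above 3.91 inches does not fail.
3. **Hypotheses.** H0: μ(violet) - μ(red) ≥ δ; H1: μ(violet) - μ(red) < δ.
4. **Supportive Secondary Evaluations, item (i).** Delete the sentence that reads p>0.05 as support for equivalency and report the interval.
5. **Rationale for Sample Size.** Give the power for the stated δ, using the reference study's actual SD.
6. **If the 5% point-estimate rule is kept,** call it a descriptive performance goal, report the 95% interval beside it and remove the statement that non-inferiority will be established. This is the realistic route if no other δ can be justified.

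The direct cost is SAP wording and one interval. Study Blinding already provides for this: "The data from each study will be de-identified and presented to the study statistician simply as" two lettered groups, so the interval can be computed as A minus B and its direction read after unmasking. The real cost is to the claim. At the 5% margin the observed violet mean would have to be about -4.25 inches, so the sponsor must either justify another margin in advance or accept a more modest conclusion. A confidence interval covers sampling error only; it does not remove bias from the unrandomised comparison with the 2014 study.

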## INDICATION FOR USE

The indication (claim) being sought through support of the results of this clinical study is:

"The Erchonia Violet ZERONA® Z6 OTC is indicated for use as a non-invasive dermatological aesthetic treatment for the reduction of body circumference."

The Erchonia Violet ZERONA® Z6 OTC is intended for Over-the-Counter (OTC) use.

The indication for use and intended use of the Erchonia Violet ZERONA® Z6 OTC is identical to the predicate device, the Erchonia ZERONA® Z6 OTC, as FDA cleared under K162578:

"The Erchonia ZERONA Z6 OTC is indicated for use as a non-invasive dermatological aesthetic treatment for the reduction of body circumference."

It is cleared for Over-the-Counter (OTC) use.

It is intended that the results of this clinical study be used to support a 510(k) submission to seek FDA clearance to market the Erchonia Violet ZERONA® Z6 OTC for the same indication for use as that cleared for the predicate device, the Erchonia ZERONA® Z6 OTC (K162578), by demonstrating that the efficacy of application of the Erchonia Violet ZERONA® Z6 OTC is non-inferior to the efficacy of application of the Erchonia ZERONA® Z6 OTC (K162578) for the reduction of body circumference of the waist, hips, and bilateral thighs when applied in the over-the-counter setting.

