## EXPECTED RESULTS

Following completion of the study treatment administration protocol, it is anticipated that compared with the Erchonia ZERONA® Z6 OTC red diode laser, application of treatment administration with the Erchonia Violet ZERONA® Z6 OTC will yield non-inferior (equivalent or superior) results with respect to mean decrease in subjects' combined waist-hips-bilateral thighs circumference measurements relative to baseline.

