In 2016, the above-mentioned predicate device, the Erchonia® ZERONA® Z6 OTC, received FDA market clearance "for use as a non-invasive dermatological aesthetic treatment for the reduction of body circumference", under 510(k) K162578.

It is intended that the results of the current proposed clinical study be used to support a 510(k) submission to FDA for clearance to market the Erchonia Violet ZERONA® Z6 OTC for the same indication for use as for the Erchonia ZERONA® Z6 OTC as cleared under K162578 by demonstrating that efficacy of application of the two devices are equivalent.

The current clinical study protocol evaluating efficacy of the Erchonia Violet ZERONA® Z6 for the reduction of body circumference is based on the efficacy protocol for the clinical study whose results were submitted in support of clearance of the predicate device, the Erchonia Zerona® Z6 OTC, under K143007.

The 510(k) submitted under K143007 additionally included a successful evaluation of Human Factors Testing and Validation. It is determined that a Human Factors Validation and Testing

study is not applicable for the Erchonia Violet ZERONA® Z6 OTC as the Operational Instructions for Use for the Erchonia Violet ZERONA® Z6 OTC and additional safety and other information contained in the Violet ZERONA® Z6 OTC Installation and Proper Use Reference Guide are identical to those for use of the predicate laser, the Erchonia ZERONA® Z6 OTC, with the only differences being the visible light output (violet compared to red) and the duration of treatment administrations (20 minutes compared to 40 minutes, which is automatically programmed into the device and cannot be altered by the user), neither of which therefore impacts the user's operation of the Violet ZERONA® Z6 OTC versus the ZERONA® Z6 OTC laser device, and therefore has no impact on the user's ability to understand or apply the instructions for use contained in the Violet ZERONA® Z6 OTC Installation and Proper Use Reference Guide or to safely or effectively apply treatments with the device relative to that demonstrated for the predicate device. The study population and all elements of the device protocol and the Violet ZERONA® Z6 OTC Installation and Proper Use Reference Guide other than the pre-programmed administration timing duration (as explained above) will be identical to that employed in evaluation of the Erchonia ZERONA® Z6 OTC device in support of K143007.

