Both the predicate and the subject laser devices have the same treatment protocol as will be evaluated for the Violet ZERONA® Z6 OTC in this current study: 6 treatments occurring over 2 weeks: 3 treatments per week; each treatment every other day.

Therefore, as usability has already been established, and all other variables of device user, use, and application are held constant, the goal of this study is solely to demonstrate that efficacy of application of violet light over 20 minutes per treatment administration procedure using the Erchonia ZERONA® Violet Z6 OTC is equivalent to application of red light over 40 minutes per treatment administration procedure using the Erchonia ZERONA® Z6 OTC with respect to reduction in body circumference attained.

The rationale for evaluating efficacy of the application of violet diodes in this current study is that prior research and preliminary testing has demonstrated that non-inferior (equivalent or superior) results with respect to body circumference reduction can be attained with application of violet light compared with application of red light using the same treatment administration protocol but with lesser treatment administration time per treatment administration – 20 minutes versus 40 minutes, respectively, which is a significant time savings to the patient.

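### The primary success criterion is stated two ways: a one-sided non-inferiority rule with no upper limit, and a window that a mean reduction above 3.91 inches misses

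*Combined protocol and SAP*

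**What the plan says.** The Primary Efficacy Outcome Evaluation section contains both rules.

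- **One-sided rule.** The research hypothesis is that violet therapy "is either equivalent to, or superior to, red diode therapy". Non-inferiority is established if the mean change "in the current study is no more than 5% less than the subject group who received treatment with the red diode laser" in the reference trial. Only a shortfall counts against the device.
- **Window rule.** The next paragraph takes the reference mean decrease of 3.72 inches, applies ±5%, and says success is met if the current mean falls in that range: "inches (-3.53 to -3.91 inches). This is defined as the maximally clinically acceptable difference for which the range of efficacy values" are close enough to be called equivalent. This has a lower and an upper limit.

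The Hypotheses section words the alternative as a device that "is NOT inferior to treatment application of the Zerona® Z6 OTC in effecting a clinically meaningful reduction in body circumference". In symbols it gives H0: mu < -3.53 and H1: mu >= -3.53. The value -3.91 does not appear there.

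The aim is also described both ways. Indication for Use seeks to show that violet "is non-inferior to the efficacy of application of the Erchonia ZERONA® Z6 OTC (K162578) for the reduction of body circumference". Expected Results anticipates that it "will yield non-inferior (equivalent or superior) results". Study Design calls the trial non-inferiority. The Regulatory Background section instead supports clearance "by demonstrating that efficacy of application of the two devices are equivalent" and says "the goal of this study is solely to demonstrate that efficacy of application of violet light over 20 minutes" is equivalent to red light over 40 minutes, although the same section also refers to non-inferior results as equivalent or superior.

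Supportive Secondary Evaluations (ii) repeats the two-sided form for the responder rate: 73% ± 5%, that is 68% to 78%.

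**The concern.** A non-inferiority criterion should not penalise a better result. Here the sentence that turns the margin into numbers puts a ceiling on success, while the sentence before it does not. For a mean reduction above 3.91 inches, the study could be reported as a success or as a failure depending on which sentence is read. That choice would be made after the data are in, in an open-label single-arm study meant to support a 510(k) submission. Blinding the statistician to group labels does not help when the rule itself is undefined.

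The formal hypotheses would normally break the tie. They cannot do so here, because on the negative change scale used for the criterion their inequalities point the wrong way.

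**Working it through.** **Inputs.** From Primary Efficacy Outcome Evaluation: reference mean change -3.72 inches, margin ±5%, printed limits -3.53 and -3.91. From Sample Size: at least 22 subjects. From Supportive Secondary Evaluations (ii): reference responder rate 73%, responder defined as a reduction of at least 3.0 inches. No SD, alpha or power is given for the primary criterion.

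**1. The plan's range reproduces.** 3.72 × 0.95 = 3.534, rounded to 3.53. 3.72 × 1.05 = 3.906, rounded to 3.91. The margin is 3.72 × 0.05 = 0.186, about 0.19 inches.

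**2. Classifying possible results (no SD needed).**

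| Mean reduction (in) | One-sided rule (≥ 3.53) | Window (3.53 to 3.91) | H1 as printed (mu ≥ -3.53) |
|---|---|---|---|
| 3.40 | fails | misses | true |
| 3.53 | passes | meets | true |
| 3.72 | passes | meets | false |
| 3.91 | passes | meets | false |
| 4.0 | passes | misses | false |
| 4.5 | passes | misses | false |

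The two rules agree up to 3.91 and disagree for every larger reduction. With reductions as negative numbers, the printed H1 admits a 3.40-inch reduction and excludes the reference value itself.

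**3. How often the conflict would arise.** An SD must be assumed. If changes are normal with mean reduction 3.72 and 73% reach 3.0 inches, then SD = (3.72 - 3.0)/z(0.73) = 0.72/0.613 = 1.17. Taking 73% as 16/22 gives 1.19. I use 1.18, with a range of 0.8 to 1.5. The standard error is 1.18/√22 = 0.252.

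For a true mean reduction m:
- one-sided rule: P = 1 - Φ((3.53 - m)/SE)
- window: P = Φ((3.91 - m)/SE) - Φ((3.53 - m)/SE)

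| True reduction | Window, SD 1.18 (SD 0.8; SD 1.5) | One-sided, SD 1.18 (SD 0.8; SD 1.5) |
|---|---|---|
| 3.53 (at the margin) | 43% (49%; 38%) | 50% (50%; 50%) |
| 3.72 (equal to red) | 55% (73%; 45%) | 77.5% (87%; 72%) |
| 4.2 | 12% (4%; 16%) | 99.6% (>99.9%; 98.2%) |
| 4.5 | 1% (0%; 3%) | >99.9% (>99.9%; 99.9%) |

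For the equal device, 0.19/0.252 = 0.755, so 22.5% of results fall below 3.53 and 22.5% above 3.91. The first half fails under either rule. The second half is the part added by the upper limit (13.3% at SD 0.8, 27.6% at SD 1.5).

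**4. Responder range (secondary).** With 22 subjects only 15, 16 or 17 responders (68.2%, 72.7%, 77.3%) lie within 68% to 78%; 18/22 = 81.8% is outside. By Binomial(22, p), a true rate of 80% meets the range 40% of the time, against 94% for at least 68%. A true rate of 73% gives 53% against 78%. The qualifying counts change with the sample size: 16 to 17 of 23, 17 to 19 of 25.

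**The case against.** The strongest reply is that the two sentences need not conflict. Each says success is met *if* its condition holds, and neither says *only if*. Read strictly, both are sufficient conditions, and a 4.5-inch reduction succeeds under the first. The stated design, the expected results and the worded hypotheses all favour the one-sided reading. That reading is possible. But the window is the only numeric statement of success, it is offered as the consequence of the margin, and no sentence says a mean beyond it succeeds.

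Second, the printed hypotheses look like a notation slip. The responder definition also attaches ≥ to a negative number (≥-3.0) to mean at least that much reduction. On that convention H1 agrees with its words and with the one-sided rule. This is probably what was intended, but it contradicts the scale on which the success range is written, so the signs still need correcting.

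Third, a better device does not always probably miss the window. At SD 1.18 a true reduction of 3.80 meets it about 53% of the time, and a miss becomes likelier than not only above about 3.84. The 4.2 and 4.5 examples are illustrative, since the active-treatment means in the plan are 3.5 and 3.7 (3.72). The SD is an assumption too. The figure closest to the plan's own data is the 22.5% for an equal device.

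Finally, both rules share the lower limit of 3.53, so the ceiling can only withhold success from a good result; it cannot let an inferior device pass. That is correct. The harm is an undefined primary outcome decision. The responder range, the hypothesis signs and the wording in Regulatory Background are secondary and do not add to its weight.

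**Conclusion.** The concern holds and should be fixed before analysis. The primary criterion is stated in two ways that give different answers for every mean reduction above 3.91 inches, and no other section resolves it. The contradiction is a matter of text and rests on no assumption.

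Its practical size depends on the unstated SD. With 22 subjects, normal sampling of the mean and SD 1.18 (0.8 to 1.5), an equal device lands in the disputed region 22.5% of the time (13% to 28%), and a device with a true reduction of 4.2 inches does so 87.5% of the time (96% to 82%). As a non-inferiority criterion the window is wrong as written. Missing the responder range does not by itself fail the study.

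**What to change.** State one rule and make the other sections agree with it.

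- **Primary Efficacy Outcome Evaluation:** replace the ±5% equivalence margin with a non-inferiority margin of 5% (0.19 inches). Delete the range and the sentence defining values as close enough. Write: *success is met if the mean reduction is at least 3.53 inches (mean change of -3.53 or lower), with no upper limit*.
- **Hypotheses:** define mu as mean change from baseline, negative meaning reduction, with H0: mu > -3.53 and H1: mu <= -3.53.
- **Supportive Secondary Evaluations (ii):** require an observed responder rate of at least 68%, kept as a proportion because 22 is a minimum. Define a responder as a change of -3.0 inches or lower.
- **Regulatory Background:** for consistency, describe the goal as non-inferior (equivalent or superior), as Expected Results does.

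The cost is wording only, with no added subjects, visits or measurements, and the sponsor's reference mean, 5% margin and 3.53 limit are kept. One consequence should be accepted openly: for a device exactly at the margin, the pass probability rises from 43% to 50% (from 49% at SD 0.8, from 38% at SD 1.5).

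This removes the contradiction only. The rule would still rest on a point estimate. A true reduction of 3.35 inches, 10% worse than 3.72, would pass 24% of the time (15% to 29%). The one-sided 95% half-width at 22 subjects (t, 21 df, reference mean treated as fixed) is 0.43 inches (0.29 to 0.55) against a margin of 0.19. The missing confidence limit must be dealt with separately.
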